2. All patients must have measurable disease as defined by irRECIST. Measurable disease is defined as 10 mm in the longest diameter by CT or MRI scan (or no less than double the slice thickness) for non- nodal lesions and ≥ 15 mm in short axis for nodal lesions, 20 mm by chest X-ray, a lymph node must be ≥ 15 mm in short axis when assessed by CT scan (CT scan slice thickness recommended to be no greater than 5 mm).
3. Must have archival tissue available for PD-L1 assessment.
4. Patients should be free of active infection requiring antibiotics (with the exception of uncomplicated UTI).

5. Patients who have the following risk factors are considered to be at increased risk for cardiac toxicities and may be enrolled only with increased monitoring (refer to Table 5, footnote 5): i) prior treatment with anthracyclines, ii) prior treatment with trastuzumab, iii) a New York Heart Association classification of II controlled with treatment, iv) prior central thoracic radiation therapy (RT), including RT to the heart.
6. Any hormonal therapy being taken as a treatment for cancer must be discontinued at least one week prior to registration. Continuation of hormone replacement therapy e.g. thyroid hormone replacement therapy is permitted.
7. Able to tolerate oral medications and no GI illnesses that would preclude absorption of olaparib.
8. Female patients, age \geq 18 years at time of study entry.
9. Have an ECOG Performance Status of 0-1. Refer to Appendix B.
10. Life expectancy of $>$ 6 months.
11. Adequate normal organ and marrow function as defined below:
 - o Hemoglobin \geq 10 g/dL (no blood transfusion in the 28 days prior to entry (olaparib guidelines))
 - o WBC $>$ 3 \times 10⁹/L
 - o Absolute neutrophil count (ANC) \geq 1.5 \times 10⁹/L (\geq 1500 per mm³)
 - o Platelet count \geq 100 \times 10⁹/L (\geq 100,000 per mm³)
 - o Serum bilirubin \leq 1.5 \times institutional upper limit of normal (ULN). This will not apply to subjects with confirmed Gilbert's syndrome (persistent or recurrent hyperbilirubinemia that is predominantly unconjugated in the absence of hemolysis or hepatic pathology), who will be allowed only in consultation with their physician
 - o AST (SGOT)/ALT (SGPT) \leq 2.5 \times institutional upper limit of normal unless liver metastases are present, in which case it must be \leq 5x ULN
 - o Creatinine \leq 1.5 \times ULN or, Serum Creatinine CL $>$ 51 mL/min (by the Cockcroft-Gault equation: see Appendix L).

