6.5 Dose Modifications and Toxicity Management

For adverse events (AEs) that are considered at least partly due to administration of durvalumab or tremelimumab or olaparib, the following dose adjustment guidance may be applied:

- Treat each of the toxicities with maximum supportive care (including holding the agent suspected of causing the toxicity where required).
- If the symptoms promptly resolve with supportive care, consideration should be given to continuing the same dose of durvalumab or tremelimumab or olaparib along with appropriate continuing supportive care. If ≥ 2 DLTs due to tremelimumab, tremelimumab will be eliminated for the Phase II expansion cohort. There will be no dose adjustment.

In addition, there are certain circumstances in which durvalumab or tremelimumab should be permanently discontinued.

Management of toxicity of durvalumab and tremelimumab

Based on the mechanism of action of durvalumab or tremelimumab leading to T-cell activation and proliferation, there is the possibility of observing immune related Adverse Events (irAEs) during the conduct of this study. Potential irAEs include immune-mediated enterocolitis, dermatitis, hepatitis, and endocrinopathies. Subjects should be closely monitored for signs and symptoms of irAEs. In the absence of an alternate etiology (e.g., infection or PD) signs or symptoms of enterocolitis, dermatitis, hepatitis, and endocrinopathy should be considered to be immune-related.

Toxicity management guidelines for immune-mediated reactions, for infusion-related reactions, and for non-immune-mediated reactions are detailed in Appendix G.

In addition, management guidelines for adverse events of special interest (AESIs) are detailed in Section 10.2. All toxicities will be graded according to NCI CTCAE v4.03.

Management of toxicity of olaparib

Any toxicity observed during the course of the study could be managed by interruption and/ or dose reduction of the dose if deemed appropriate by the Investigator. Repeat dose interruptions are allowed as required, for a maximum of 14 days on each occasion. If the interruption is any longer than this the AstraZeneca study team must be informed. Olaparib must be interrupted until the patient recovers completely or the toxicity reverts to the National Cancer Institute (NCI) Common Terminology Criteria for Adverse Events (current version) grade 1 or less.

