Where toxicity reoccurs following re-challenge with olaparib, and where further dose interruptions are considered inadequate for management of toxicity, then the patient should be considered for dose reduction or must permanently discontinue treatment with olaparib. Dose de-escalation will be to 250 mg BID and then to 200 mg BID if needed.

Treatment must be interrupted if any NCI-CTCAE grade 3 or 4 adverse event occurs which the Investigator considers to be at least possibly related to administration of olaparib.

Management of anemia

Adverse events of anemia CTCAE grade 1 or 2 (Hemoglobin (Hb) > 8 g/dL) should be investigated and managed as deemed appropriate by the investigator with or without interruption of study drug or change in dose, taking into account previous history of anemia. Common treatable causes of anemia (e.g., iron, vitamin B12 or folate deficiencies and hypothyroidism) should be excluded. In some cases, management of anemia may require blood transfusions. However, if a patient develops anemia CTCAE grade 3 (Hb < 8 g/dL) or worse, study treatment should be interrupted for up to maximum of 4 weeks to allow for bone marrow recovery and the patient should be managed appropriately. Study treatment can be restarted at the same dose if Hb has recovered to > 10 g/dL. Any subsequently required anemia related interruptions, considered likely to be dose related, or coexistent with newly developed neutropenia, and or thrombocytopenia, will require study treatment dose reductions by 250 mg bd as a first step and to 200 mg bd as a second step.

If a patient has been treated for anemia with multiple blood transfusions without study treatment interruptions and becomes blood transfusion dependent as judged by investigator, study treatment should be permanently discontinued.

Management of neutropenia and leukopenia

Adverse event of neutropenia and leukopenia should be managed as deemed appropriate by the investigator with close follow up and interruption of study drug if CTC grade 3 or worse neutropenia occurs. Primary prophylaxis with Granulocyte colony-stimulating factor (G-CSF) is not recommended, however, if a patient develops febrile neutropenia, study treatment should be stopped and appropriate management including G-CSF should be given according to local hospital guidelines. Please note that G-CSF should not be used within at least 24 h of the last dose of study treatment.

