Study treatment can be restarted at the same dose if an adverse event of neutropenia or leukopenia have been recovered up to CTC AE grade >1 (ANC $> 1.5 \times 10^9/L$). Growth factor support should be stopped at least 24h before restarting study drug (7 days for pegylated G-CSF).

Any subsequent interruptions will require study treatment dose reductions.

Management of thrombocytopenia

An adverse event of thrombocytopenia should be managed as deemed appropriate by the investigator. If a patient develops thrombocytopenia CTCAE grade 3 or worse study treatment should be interrupted for a maximum of 4 weeks. In some cases, management of thrombocytopenia may require platelet transfusions. Platelet transfusions should be done according to local hospital guidelines.

Management of prolonged hematological toxicities while on study treatment

If a patient develops prolonged hematological toxicity such as:

- ≥ 2 week interruption/delay in study treatment due to CTC grade 3 or worse anemia and/or development of blood transfusion dependence
- ≥ 2 week interruption/delay in study treatment due to CTC grade 3 or worse neutropenia (ANC $< 1 \times 10^9/L$)
- ≥ 2 week interruption/delay in study treatment due to CTC grade 3 or worse thrombocytopenia (Platelets $< 50 \times 10^9/L$)

Weekly differential blood counts including reticulocytes (calculate reticulocyte index (RI), RI = reticulocyte count x hematocrit (Hct)/normal Hct; a value of 45 is usually used for normal Hct) and peripheral blood smear should be performed. If any blood parameters remain clinically abnormal after 4 weeks of dose interruption, the patient should be referred to hematologist for further investigations. Bone marrow analysis and/or blood cytogenetic analysis should be considered at this stage according to standard hematological practice.

Myelodysplastic syndrome and/or Acute Myeloid Leukemia (MDS/AML is an important potential risk for olaparib. Development of a confirmed MDS or other clonal blood disorder should be

reported as an SAE and full reports must be provided by the investigator to AstraZeneca Patient Safety. Study treatment should be discontinued if diagnosis of MDS/AML is confirmed.

The dose of olaparib **must not** be adjusted under any other circumstances unless the AstraZeneca Study Physician gives prior agreement.

Management of new or worsening pulmonary symptoms

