	
(Colitis: abdominal pain; mucus or blood in stool) (Perforation: symptomatic; medical intervention indicated*)
 
* “medical intervention” is not invasive
	
 If toxicity improves to Grade ≤ 1, then study drug/study regimen can be resumed after completion of steroid taper. 	
(e.g., American Dietetic Association colitis diet), and loperamide and/or budesonide.
 
 Promptly start prednisone 1 to 2 mg/kg/day PO or IV equivalent. If event is not responsive within 3 to 5 days or worsens despite prednisone at 1 to 2 mg/kg/day PO or IV equivalent, GI consult should be obtained for consideration of further workup, such as imaging and/or colonoscopy, to confirm colitis and rule out perforation, and prompt treatment with IV methylprednisolone 2 to 4 mg/kg/day started. If still no improvement within 3 to 5 days despite 2 to 4 mg/kg IV methylprednisolone, promptly start immunosuppressives such as infliximab at 5 mg/kg once every 2 weeks a. Caution: it is important to rule out bowel perforation and refer to infliximab label for general guidance before using infliximab. Consider, as necessary, discussing with study physician if no resolution to Grade ≤ 1 in 3 to 4 days. Once the patient is improving, gradually taper steroids over ≥ 28 days and consider prophylactic antibiotics, antifungals, and anti-PJP treatment (refer to current NCCN guidelines for treatment of cancer-related infections).^a
	
Grade 3 or 4 (Grade 3: Diarrhea stool frequency of ≥ 7 over baseline per day; Grade 4 Diarrhea: life threatening consequences)
	
Permanently discontinue study drug/study regimen- for Grade 3 if toxicity does not improve to Grade < 1 within 14 days; study drug/study regimen can be resumed after completion of steroid taper.
 
Grade 4
	
For Grade 3 or 4:
 
 Promptly initiate empiric IV methylprednisolone 2 to 4 mg/kg/day or equivalent. Monitor stool frequency and volume and maintain hydration. Urgent GI consult and imaging and/or colonoscopy as appropriate.

Specific Immune-mediated Reactions			
Adverse Events	Severity Grade of the Event (NCI CTCAE version 4.03)	Dose Modifications	Toxicity Management

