
Hepatitis (elevated LFTs) Infliximab should not be used for management of immune-related hepatitis.
 
PLEASE SEE shaded area immediately below this section to find guidance for management of "Hepatitis (elevated LFTs)" in HCC patients
	
Any Elevations in AST, ALT or TB as Described Below
 
(AST or ALT $> 3 \times$ ULN if baseline normal, 1.5-3.0\timesbaseline if baseline abnormal; and/or TB $> 1.5 \times$ ULN if baseline normal, $> 1.0-1.5 \times$baseline if baseline abnormal)
 
(AST or ALT > 3 to $5 \times$ ULN if baseline normal, $> 3-5 \times$baseline if baseline abnormal; and/or TB > 1.5 to $3.0 \times$ ULN if baseline normal, $> 1.5-3.0 \times$baseline if baseline abnormal)
	
General Guidance
 
No dose modifications.
 
 If it worsens, then treat as described for elevations in the row below. 
Hold study drug/study regimen dose until resolution to AST or ALT $\leq 3.0 \times$ULN and/or TB $\leq 1.5 \times$ULN if baseline normal, or to AST or ALT $\leq 3.0 \times$baseline and/or TB $\leq 1.5 \times$baseline if baseline abnormal.
 
 If toxicity worsens, then treat as described for elevation in the row below. If toxicity improves to AST or ALT $\leq 3.0 \times$ULN and/or TB $\leq 1.5 \times$ULN if baseline normal, or to AST or ALT $\leq 3.0 \times$baseline and/or TB $\leq 1.5 \times$baseline if baseline abnormal in 1 to 2 days, consider, as necessary, discussing with study physician. 	
For Any Elevations Described:
 
 Monitor and evaluate liver function test: AST, ALT, ALP, and TB. Evaluate for alternative etiologies (e.g., viral hepatitis, disease progression, concomitant medications). 
 Continue LFT monitoring per protocol. 
 Regular and frequent checking of LFTs (e.g., every 1 to 2 days) until elevations of these are improving or resolved. If no resolution to AST or ALT $\leq 3.0 \times$ULN and/or TB $\leq 1.5 \times$ULN if baseline normal, or to AST or ALT $\leq 3.0 \times$baseline and/or TB $\leq 1.5 \times$baseline if baseline abnormal in 1 to 2 days, consider, as necessary, discussing with study physician.

Specific Immune-mediated Reactions			
Adverse Events	Severity Grade of the Event (NCI CTCAE version 4.03)	Dose Modifications	Toxicity Management

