	Grade 3 or 4	
For Grade 3 or 4 endocrinopathy other than hypothyroidism and Type I diabetes mellitus, hold study drug/study regimen dose until endocrinopathy symptom(s) are controlled.
 
Study drug/study regimen can be resumed once event stabilizes and after completion of steroid taper.
 
Patients with endocrinopathies who may require prolonged or continued steroid replacement (e.g. adrenal insufficiency) can be treated with study drug/study regimen on the following conditions:
 
 1. The event stabilizes and is controlled 2. The patient is clinically stable as per investigator or treating physician's clinical judgement 3. Doses of prednisone are < 10 mg/day or equivalent 	
For Grade 3 or 4:
 
 • Consult endocrinologist to guide evaluation of endocrine function and, as indicated by suspected endocrinopathy and as clinically indicated, consider pituitary scan. Hospitalization recommended • For all patients with abnormal endocrine work up, except those with isolated hypothyroidism or Type I DM, and as guided by an endocrinologist, promptly initiate empiric IV methylprednisolone 1 to 2 mg/kg/day or equivalent, as well as relevant hormone replacement (e.g., hydrocortisone, sex hormones). • For adrenal crisis, severe dehydration, hypotension, or shock, immediately initiate IV corticosteroids with mineralocorticoid activity. • Isolated hypothyroidism may be treated with replacement therapy, without study drug/study regimen interruption, and without corticosteroids. • Isolated Type I diabetes mellitus may be treated with appropriate diabetic therapy, without study drug/study regimen interruption, and without corticosteroids. • Once patients on steroids are improving, gradually taper immunosuppressive steroids (as appropriate and with guidance of endocrinologist) over ≥28 days and consider prophylactic antibiotics, antifungals, and anti-PJP treatment (refer to current NCCN guidelines for treatment of cancer-related infections).^a

Specific Immune-mediated Reactions			
Adverse Events	Severity Grade of the Event (NCI CTCAE version 4.03)	Dose Modifications	Toxicity Management

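### Section 6.5: the grade in the same-dose restart sentence for neutropenia or leukopenia runs opposite to the olaparib release rule and does not fit its own ANC bracket; check the sign and correct it

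*Combined protocol and SAP*

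**What the plan says.** Section 6.5 (Dose Modifications and Toxicity Management) has three instructions that bear on restarting after a low neutrophil or white-cell count.

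- **General olaparib hold.** "Treatment must be interrupted if any NCI-CTCAE grade 3 or 4 adverse event occurs", where the investigator considers the event at least possibly related to olaparib.
- **General olaparib release.** This is mandatory: the drug stays on hold until full recovery, or until "the toxicity reverts to the National Cancer Institute (NCI) Common Terminology Criteria for Adverse Events (current version) grade 1 or less".
- **Neutropenia and leukopenia paragraph.** Study drug is interrupted for Grade 3 or worse neutropenia. Study treatment can then be restarted at the same dose "if an adverse event of neutropenia or leukopenia have been recovered up to CTC AE grade >1", with a bracket giving ANC above 1.5 × 10⁹/L.

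The subsection on prolonged hematological toxicities, also in 6.5, equates Grade 3 or worse neutropenia with ANC below 1 × 10⁹/L. Section 5.1, criterion 11, sets the entry limit for ANC at 1.5 × 10⁹/L or more.

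**The concern.** A restart rule should name the level to which a toxicity must fall before dosing resumes. Here the grade names the side on which dosing should stay on hold. Two instructions under the same olaparib heading then disagree: one is mandatory and general, the other permissive and specific to the toxicity. Section 6.5 does not say which prevails.

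This is an operative dosing threshold for a drug whose listed effects include decreased neutrophils and leukopenia (Section 1.3.2.4), in a trial run at several sites. The stake is that a site turns to the toxicity-specific paragraph, as sites tend to do, and takes from it a permission that the general rule withholds.

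**Working it through.** No design figure is involved, so this is a check of consistency using the protocol's own definitions.

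**Inputs**

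| Item | Value | Place |
|---|---|---|
| Order of grades | higher is more severe | 10.1.2 |
| General release | full recovery, or grade 1 or less | 6.5, olaparib toxicity |
| Restart sentence, grade part | above 1 | 6.5, neutropenia and leukopenia |
| Restart sentence, bracket | ANC > 1.5 × 10⁹/L | same sentence |
| Grade 3 or worse neutropenia | ANC < 1 × 10⁹/L | 6.5, prolonged hematological toxicities |
| Entry ANC | ≥ 1.5 × 10⁹/L | 5.1, criterion 11 |

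**Step 1: grade part against the general rule.** The general rule releases at {recovered, 1}. The grade part describes everything above 1. The two sets have no member in common. Taken literally, the grade part would even refuse a same-dose restart to a patient who had fully recovered, which cannot be intended.

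**Step 2: grade part against its own bracket.** The grade part admits Grade 3 or worse, which the protocol places below 1.0 × 10⁹/L. The bracket requires more than 1.5 × 10⁹/L. The gap is 1.5 − 1.0 = 0.5 × 10⁹/L, so no ANC meets both. The two halves of the sentence disagree, and the full condition cannot be met by a patient with Grade 3 or worse neutropenia. An ANC between 1.0 and 1.5 × 10⁹/L is also blocked by the bracket, whatever grade it carries.

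**Step 3: intended direction.** Four things agree on it: the sentence speaks of recovery; the bracket figure equals the entry limit for ANC; the general olaparib rule releases at grade 1 or less; and the table of non-immune-mediated reactions in Appendix G holds drug at Grade 2 and Grade 3 until Grade 1 or lower, or baseline. That table is written for the antibodies, so it supports the direction only.

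**Step 4: what the bracket does not cover.** The sentence treats neutropenia and leukopenia together but gives only a neutrophil value. If a patient has leukopenia and ANC above 1.5 × 10⁹/L, the bracket is met and does not constrain the leukopenia grade. The paragraph's own interruption trigger names neutropenia only. The hold for possibly related Grade 3 or 4 leukopenia, and release at grade 1 or less, therefore come from the general olaparib rules alone.

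**Step 5: after correction.** With grade 1 or less and ANC above 1.5 × 10⁹/L, the sentence agrees with the general release rule, with its own bracket and with the Grade 3 interruption trigger. No other instruction changes.

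**The case against.** **The sign may be a reading error.** This is the strongest point against, and it cannot be excluded. The text was read from PDF by a program, and comparators look doubtful in Appendix G. In the hepatitis table, the row with no dose modification is shown as AST or ALT above 3 × ULN, although the next row, which holds drug, starts at the same limit. The Grade 3 colitis entry reads "for Grade 3 if toxicity does not improve to Grade < 1 within 14 days" where the Grade 2 entry has Grade 1 or lower. The endocrinopathy entry for Grade 3 or 4 reads "Doses of prednisone are < 10 mg/day or equivalent" where the Grade 2 entry allows exactly 10 mg. On the other side, greater-or-equal and less-or-equal signs come through correctly in many places, including the lines on two-week interruptions in the same part of Section 6.5. The documents do not settle it. What stands is that the source page must be checked first. A reader might count the Appendix G entries as further cases of the same defect. They are not: they bear only on how far a single comparator in this text can be trusted.

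**The sentence already fixes the direction.** This largely stands for neutropenia. A reader might infer that the rule releases patients at Grade 2, 3 or 4, or that restart is allowed with no recovery at all. Neither follows. Both readings drop the ANC bracket and the requirement that the event has recovered, and Step 2 shows that Grade 3 or worse neutropenia cannot meet the full condition.

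**Other rules cover it.** The general hold and release rules are mandatory and the restart sentence is only permissive, and a permission does not cancel a requirement. That is the better reading, and it keeps the risk small. It does not remove the conflict for a site working from the toxicity-specific paragraph, since the protocol states no order of precedence.

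**Conclusion.** The point holds as a minor error in a safety instruction. As the text reads, the grade wording is the opposite of the mandatory release rule and does not fit the sentence's own bracket, and the protocol itself shows what was meant.

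The practical risk is confined to leukopenia with ANC above 1.5 × 10⁹/L at a site that follows the specific permission over the general rule. The documents give no basis for saying how often that would arise, and no frequency is claimed. Sample size, power and alpha are untouched.

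The conclusion assumes that the source page carries the same sign as the text reviewed. If it does not, the point falls away. Confidence is medium for that reason.

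**What to change.** Check the sign in the neutropenia and leukopenia paragraph of Section 6.5 against the source page. If it is printed as a grade above 1, change it to grade 1 or less and keep ANC above 1.5 × 10⁹/L. No separate white-cell value is needed, because the general olaparib rule already sets grade 1 or less for leukopenia.

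The cost is one look at the source page and, if confirmed, one sentence in an amendment or a clarification sent to sites.

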6.6 Restrictions, General Concomitant Medication and Supportive Care

6.6.1 Restrictions during the study

Contraception

The following restrictions apply while the patient is receiving study treatment and for the specified times before and after:

Female patient of child-bearing potential

Females of childbearing potential who are sexually active with a non-sterilized male partner must use at least 1 **highly** effective method of contraception (Table 2) from the time of screening and must agree to continue using such precautions for 180 days after the last dose of durvalumab + tremelimumab combination therapy or 90 days after the last dose of durvalumab monotherapy. Non-sterilized male partners of a female patient must use male condom plus spermicide throughout this period. Cessation of birth control after this point should be discussed with a responsible physician. Not engaging in sexual activity for the total duration of the drug treatment and the drug washout period is an acceptable practice; however, periodic abstinence, the rhythm method, and the withdrawal method are not acceptable methods of birth control. Female patients should also refrain from breastfeeding throughout this period.

N.B.: Females of childbearing potential are defined as those who are not surgically sterile (i.e., bilateral tubal ligation, bilateral oophorectomy, or complete hysterectomy) or post-menopausal.

Women will be considered post-menopausal if they have been amenorrheic for 12 months without an alternative medical cause. The following age-specific requirements apply:

- Women <50 years of age would be considered post-menopausal if they have been amenorrheic for 12 months or more following cessation of exogenous hormonal treatments and if they have luteinizing hormone and follicle-stimulating hormone levels in the post-menopausal range for the institution or underwent surgical sterilization (bilateral oophorectomy or hysterectomy).
- Women ≥50 years of age would be considered post-menopausal if they have been amenorrheic for 12 months or more following cessation of all exogenous hormonal treatments, had radiation-induced menopause with last menses >1 year ago, had chemotherapy-induced menopause with last menses >1 year ago, or underwent surgical sterilization (bilateral oophorectomy, bilateral salpingectomy or hysterectomy).

Highly effective methods of contraception, defined as one that results in a low failure rate (i.e., less than 1% per year) when used consistently and correctly, are described in Table 2. Note that some contraception methods are not considered highly effective (e.g. male or female condom with or without spermicide; female cap, diaphragm, or sponge with or without spermicide; non-copper containing intrauterine device; progestogen-only oral hormonal contraceptive pills where inhibition of ovulation is not the primary mode of action [excluding Cerazette/desogestrel which is considered highly effective]; and triphasic combined oral contraceptive pills).

Table 2 Highly Effective Methods of Contraception (<1% failure rate)

Barrier/Intrauterine methods	Hormonal Methods

• Copper T intrauterine device• Levonorgesterel-releasing intrauterine system (e.g., Mirena®)^a	
• Etonogestrel implants (e.g. Implanon or Norplant)• Intravaginal device (e.g., ethinylestradiol and etonogestrel)• Medroxyprogesterone injection (e.g., Depo-Provera)• Normal and low dose combined oral contraceptive pill• Norelgestromin/ethinylestradiol transdermal system• Cerazette (desogestrel)

^a This is also considered a hormonal method

Blood Donation

Subjects should not donate blood while participating in this study, or for at least 90 days following the last dose of durvalumab or tremelimumab or olaparib concomitant treatments.

Food Intake Restrictions

Avoid grapefruit and Seville oranges during olaparib treatment and 3 months following the last dose of trial treatment, which may increase olaparib plasma concentrations. Olaparib tablet formulation can be taken with no regard to food.

The Principal Investigator must be informed as soon as possible about any medication taken from the time of screening until the end of the clinical phase of the study (final study visit). Any concomitant medication(s), including herbal preparations, taken during the study will be recorded in the eCRF.

Restricted, prohibited, and permitted concomitant medications are described in the following tables.

